#### 1. For equivalence of DVD programme and face-to-face programme.

In a previous HTA study comparing different pharmacotherapy options in asthma (the ELEVATE study, Controlled-Trials.com number, ISRCTN99132811, Price et al, 2011), treatments were deemed to be equivalent if the 95% CI for mean difference between groups in AQLQ was wholly included between -0.3 and +0.3. Our sample size calculation for equivalence therefore uses the same equivalence boundary (i.e. between -0.3 and +0.3). However, we have assumed that the SD of the between group difference in AQLQ will be a conservative 25% smaller (i.e. 0.77) than that reported in our GLAD study (1.03). The justification for this is that the proposed equivalence analysis will compare two breathing training interventions as opposed to a breathing intervention versus usual care in the GLAD study. Since this is an equivalence study, as opposed to a non-inferiority study, a two-tailed 5% significance level was used in the calculations (29). Following published guidelines (30), the equivalence margin was therefore selected to be 'the largest difference that can be judged to be clinically acceptable and should be smaller than differences observed in superiority trials of the active comparator'.

Using Nquery 7.0 (specifically the MTEOU-1 two group t-test of equivalence in means – unequal n's program), the following justification of the sample size is obtained:

Sample sizes of 210 in the DVD breathing retraining group and 105 in the 'face-to-face' physiotherapy group are required to assess treatment equivalence with 90% power using an equivalence boundary for AQLQ of 0.3. This assumes: that the expected between group difference in mean AQLQ is zero; a two tailed 5% significance level; common standard deviation for AQLQ of 0.77 and a lower/upper limit of -0.3/+0.3 for the 95% confidence interval of the between group difference in AQLQ.

In the unlikely event that the between group AQLQ standard deviation is higher than our estimated 0.77, assuming all other parameters stayed the same, we would still have 80% power to declare equivalence between the DVD breathing retraining group and the 'face-to-face' physiotherapy group as long as the between group SD was no higher than 0.89.

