## 2. For superiority of both the DVD-delivered and the face-to-face programme over 'usual care'

For the superiority sample size calculations, there is no widely acceptable MCID for between group change in AQLQ, although the MCID for within person change in AQLQ is reported to be 0.5 (SD 0.41) (31). Therefore, we approached the superiority sample size calculation in two ways. Firstly, using the published within person MCID of 0.5 and secondly, using estimates from the GLAD study, a between group mean (SD) difference in AQLQ at 6 months of 0.38 (1.03). Using an MID of 0.5

Nquery 7.0 (specifically the MTTOU-1 two group t-test of equal means – unequal n's program) shows that a two group t-test with a 5% one-sided significance level will have 90% power to detect a difference in mean AQLQ of 0.5 or greater, assuming that the common standard deviation is 0.41, when the

BREATHE Page 26 of 35 Protocol v6 01-08-2014

sample sizes are 10 in the face-to-face breathing retraining and 20 in the 'usual care' groups.

Similarly, a two group t-test with a 5% one-sided significance level will have 90% power to detect a difference in mean AQLQ of 0.5 or greater, assuming that the common standard deviation is 0.41, when the sample size is 13 in each of the DVD-delivered and 'usual care' groups.

Using an MID of 0.38

A two group t-test with a 5% one-sided significance level will have 92% power to detect a difference in mean AQLQ of 0.38 or greater, assuming that the common standard deviation is 1.03, when the sample sizes are 105 in the face-to-face breathing retraining and 210 in the 'usual care' groups.

Similarly, a two group t-test with a 5% one-sided significance level will have 90% power to detect a difference in mean AQLQ of 0.38 or greater, assuming that the common standard deviation is 1.03, when the sample size is 130 in each of the DVD-delivered and 'usual care' groups.

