#### Statistical Analysis:

#### 1. Analysis plan for equivalence study

Analysis and reporting of the equivalence comparison will follow published guidelines. It is known that full analysis set or ITT may lead to bias (from protocol violators, withdrawals and dropouts) and a resultant increase in type 1 error risk. Therefore, for the equivalence study, an ITT and a per protocol analysis will run simultaneously, neither having supremacy over the other. They should hopefully lead to similar conclusions giving the study a robust interpretation.

A 95% CI will be constructed for the mean difference in 12 month total AQLQ score between the DVD arm and the 'face-to-face' breathing retraining arm. Since the equivalence boundary is set at 0.3, equivalence will be declared if the 95% CI is wholly included between -0.3 and +0.3. If equality is not evident, then ANCOVA will be used to examine whether the 'face-to-face' breathing retraining arm is superior to the DVD arm via examination of the difference (and 95% confidence interval) of 12 month total AQLQ score (and each of the four domain scores) before and after adjustment for baseline AQLQ score and potential covariates such as age, gender, practice, smoking status etc.

BREATHE Page 27 of 35 Protocol v6 01-08-2014

ANCOVA will also be used to analyse the difference (and 95% confidence interval) for the secondary outcome measures (ACQ, lung function, fraction of exhaled nitric oxide, EuroQOL, anxiety and depression score, hyperventilation and patient enablement scores) at 12 months before and after adjustment for baseline values and potential confounders. Since we have data on AQLQ, ACQ and HADS at four time points (baseline, 3, 6 and 12 months) a repeated measures analysis will be used to examine change in each of these outcomes over time. For those secondary outcomes which involve count data (i.e. oral corticosteroid courses, bronchodilator use, asthma related healthcare resource use), Poisson regression analyses with a log link function will be performed to give rate ratios (and their 95% confidence intervals) in the DVD and 'face-to-face' breathing retraining arm both before and after adjustment for potential confounders such as smoking status and sociodemographic factors.

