#### 2. Analysis plan for superiority study

Baseline comparability between the three arms of the trial will be evaluated by examination of summary statistics (the mean and standard deviation or median and interquartile range for continuous variables, dependent on their distribution, and the number and percentage for categorical variables). In accordance with CONSORT guidelines, all comparative analysis will be conducted on an intention to treat (ITT) basis with a per protocol analysis performed as a sensitivity analysis.

For the primary outcome, analysis of covariance (ANCOVA) will be used to examine the 12-month total AQLQ score (and each of the four domain scores) across the three arms with initial adjustment for baseline AQLQ score and then for other potential covariates such as age, gender, practice, smoking status etc. Pair wise comparisons of AQLQ differences will be examined between the 'usual care' arm and each of the DVD and 'face-to-face' breathing retraining arms via calculation of one sided 95% confidence intervals. If the confidence interval includes +0.3 then superiority of either the DVD or 'face-to-face' breathing retraining arms over usual care will be rejected.

In a similar way, ANCOVA will also be used to analyse the continuous secondary outcome measures (ACQ, lung function, fraction of exhaled nitric oxide, EuroQOL, anxiety and depression score, hyperventilation and patient enablement scores). Since we have data on AQLQ, ACQ and HADS at four time points (baseline, 3, 6 and 12 months) a repeated measures analysis will be used to examine change in each of these outcomes over time. The 'usual care' arm will be compared to each of the DVD and 'face-to-face' breathing retraining arms in turn.

For those secondary outcomes which involve count data (i.e. oral corticosteroid courses, bronchodilator use, asthma related healthcare resource use), Poisson regression analyses with a log link function will be performed to give rate ratios in the DVD and 'face-to-face' breathing retraining arm compared to 'usual care' both before and after adjustment for potential confounders such as smoking status and sociodemographic factors.

BREATHE Page 28 of 35 Protocol v6 01-08-2014

Data and all appropriate documentation will be stored for a minimum of 5 years after the completion of the trial, including the follow-up period.

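### Superiority over usual care is judged by one-sided 95% intervals but face-to-face v DVD by an ordinary 95% interval on the same outcome, with no reason given for the laxer standard

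*Protocol*

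**What the plan says.** All references are to protocol section 8.1.

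- **Usual-care contrasts, analysis** (Analysis plan for superiority study): DVD and face-to-face are each compared with usual care "via calculation of one sided 95% confidence intervals". The next sentence sets the boundary: "If the confidence interval includes +0.3 then superiority of either the DVD or 'face-to-face' breathing retraining arms over usual care will be rejected".
- **Usual-care contrasts, sample size** (superiority subsection): "A two group t-test with a 5% one-sided significance level will have 92% power to detect a difference in mean AQLQ of 0.38 or greater", with SD 1.03, "when the sample sizes are 105 in the face-to-face breathing retraining and 210 in the 'usual care' groups". The DVD calculation uses the same level and gives 130 per arm for 90% power.
- **Face-to-face v DVD, analysis** (Analysis plan for equivalence study): "equivalence will be declared if the 95% CI is wholly included between -0.3 and +0.3". If that fails, ANCOVA asks whether face-to-face is "superior to the DVD arm via examination of the difference (and 95% confidence interval) of 12 month total AQLQ score". Neither the sidedness of this interval nor the value it must exclude is written down.
- **Face-to-face v DVD, sample size** (equivalence subsection): "a two-tailed 5% significance level was used in the calculations", with the equivalence aim given as the reason.

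No reason is offered for one-sided 5% in the usual-care contrasts.

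**The concern.** Three pairwise contrasts are made on one primary outcome. The two against usual care, which include the DVD comparison that the protocol calls its focus, are allowed 5% error in the tested direction. The third, on its ordinary reading, is allowed 2.5%. The more permissive standard thus falls on the comparison that matters most.

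A one-sided interval also has no limit on the other side. Readers would not learn how large the benefit could plausibly be, and the analysis could not show that a programme makes AQLQ worse. The protocol does not treat harm as impossible: section 6.3.2 asks for anxiety, depression, breathing and chest-symptom events to be recorded.

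The secondary outcomes are left unclear. The equivalence plan gives them a 95% interval. The superiority plan says they are handled in a similar way to the primary outcome, straight after the one-sided rule.

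**Working it through.** **Inputs** (protocol 8.1): difference 0.38 and SD 1.03 from the earlier face-to-face trial; 210 DVD, 210 usual care and 105 face-to-face analysed; boundary +0.3.

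**Standard errors**, SE = SD × √(1/n₁ + 1/n₂):
- 210 v 210: 1.03 × √(2/210) = 0.1005
- 105 v 210: 1.03 × √(1/105 + 1/210) = 0.1231

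**1. Reproduce the stated power** (noncentral t, null of zero, true difference 0.38):

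| Comparison | one-sided 5% | two-sided 5% | protocol states |
|---|---|---|---|
| 105 v 210 | 92.4% | 86.8% | 92% |
| 130 v 130 | 90.7% | 84.2% | 90% |
| 210 v 210 | 98.3% | 96.5% | not stated |

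The stated figures are therefore one-sided 5% against zero. The smallest size for 90% power is 127 per arm one-sided and 156 per arm two-sided. Both are below 210.

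**2. Results that sidedness decides under the written rule.** The lower limit must exceed 0.3, so the observed difference must exceed 0.3 + t × SE.
- 210 v 210: one-sided 0.3 + 1.6485 × 0.1005 = 0.466; two-sided 0.3 + 1.9657 × 0.1005 = 0.498.
- 105 v 210: one-sided 0.3 + 1.6497 × 0.1231 = 0.503; two-sided 0.3 + 1.9676 × 0.1231 = 0.542.

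Differences between the two values in each pair count as superior with the one-sided interval and not with the two-sided one.

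**3. Where the 5% applies.** At a true difference of 0.3 the chance of declaring superiority is 5% one-sided and 2.5% two-sided. At a true difference of zero, with the one-sided rule, the normal approximation gives 1 − Φ(0.3/SE + 1.645):
- 210 v 210: 0.3/0.1005 + 1.645 ≈ 4.63, about 0.0002%
- 105 v 210: 0.3/0.1231 + 1.645 ≈ 4.08, about 0.002%

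**4. Power under the +0.3 rule at a true 0.38.** The margin over the boundary is 0.38 − 0.3 = 0.08.

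| Comparison | one-sided 5% | two-sided 5% |
|---|---|---|
| 210 v 210 | about 20% | about 12% |
| 105 v 210 | about 16% | about 9% |

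These use the unadjusted SD. Baseline adjustment by ANCOVA may reduce it, by an amount the protocol does not give. As an illustration, at SD 0.77 the one-sided figures are 28% and 22%.

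**The case against.** The other side has a good case. The usual-care hypothesis is directional, the one-sided choice is prespecified, and sample size and analysis agree on it. The two-tailed level in the sample-size section is stated for equivalence, a different question, and does not bind a superiority test. All of this stands, so the choice is not an internal contradiction. It does not supply a reason for the laxer level.

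Three stronger readings are tempting and are not supported:

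- **That a useless DVD has a 5% chance of being declared superior.** The +0.3 boundary is unconditional, and under no effect that chance is about 0.0002% (DVD) or 0.002% (face-to-face). The written rule is harder to meet than a two-sided interval that need only exclude zero: 0.466 against 0.198 (1.9657 × 0.1005) for the DVD.
- **That one borderline result could be superior under one plan and not under the other.** Each contrast appears in one plan only.
- **That the secondary outcomes are definitely one-sided.** The wording carries over ANCOVA and does not say which interval goes with it. A +0.3 AQLQ boundary could not sensibly apply to lung function or exhaled nitric oxide.

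The two-sided reading of the face-to-face v DVD interval is itself an inference, though the ordinary one for an unqualified 95% interval.

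**Conclusion.** The point holds as an unjustified difference in standard of evidence between contrasts on one primary outcome. One-sided intervals allow 5% rather than 2.5% error at the tested boundary of +0.3. The results affected are narrow bands of observed difference, 0.466 to 0.498 for the DVD and 0.503 to 0.542 for face-to-face, at SD 1.03 and the planned analysed numbers; a smaller adjusted SD would lower and narrow them. The missing upper limit affects every usual-care result, whatever its size.

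The planned size survives a two-sided level when power is taken against zero. It does not deliver the stated power for the decision rule as written: 92% (105 v 210) and 90% (130 per arm) are computed against zero, while superiority is judged against +0.3. A change of sidedness alone would leave that mismatch in place.

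**What to change.** In the superiority analysis plan, use two-sided 95% intervals for both usual-care AQLQ contrasts. State that the continuous secondary outcomes also use two-sided 95% intervals, and state explicitly that the face-to-face v DVD interval is two-sided.

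In the superiority sample-size text, replace the one-sided 5% level with two-sided 5%. Restate power for 0.38 and SD 1.03, labelled as against a null of zero: about 96% at 210 v 210 and 87% at 105 v 210, with 156 rather than 130 per arm for 90%. The calculations at 0.5 and SD 0.41 need the same edit: power at the stated sizes falls from 92.3% to 86.0% (10 v 20) and from 91.5% to 84.7% (13 v 13), with no effect on the planned size.

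At the same time, reconcile the null used for power with the +0.3 boundary. Either superiority is judged against zero, and the restated power applies, or +0.3 is kept and power is given for that rule.

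**Cost:** wording and restated power, with no extra patients. Stated face-to-face v usual care power against zero falls from 92% to 87%. If +0.3 is kept, power at a true 0.38, already low, falls from about 20% to 12% (DVD) and from 16% to 9% (face-to-face).

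### The superiority rule tests against +0.3 AQLQ units, but the superiority sample size was calculated against zero, so the stated power does not belong to the rule that decides the comparison

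*Protocol*

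**What the plan says.** Protocol section 8.1, Sample Size, item 2 (superiority) uses the nQuery routine for a "two group t-test of equal means", so the null difference is zero. It plans on two scenarios.

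- **Difference 0.38, SD 1.03**, from the investigators' earlier breathing-training trial. For face-to-face (105) against usual care (210): "A two group t-test with a 5% one-sided significance level will have 92% power to detect a difference in mean AQLQ of 0.38 or greater". For the DVD against usual care, with 130 per arm, the test "will have 90% power to detect a difference in mean AQLQ of 0.38 or greater, assuming that the common standard deviation is 1.03".
- **Difference 0.5, SD 0.41**, from a published minimal important difference for change within a person. This needs 13 per arm for the DVD, and 10 against 20 for face-to-face.

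The Summary that follows sets the analysed numbers at 210 DVD, 210 usual care and 105 face-to-face.

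Section 8.1, Statistical Analysis, item 2 (superiority) compares each intervention with usual care by ANCOVA, "via calculation of one sided 95% confidence intervals", and then gives the decision rule: "If the confidence interval includes +0.3 then superiority of either the DVD or 'face-to-face' breathing retraining arms over usual care will be rejected".

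The value 0.3 appears in item 1 of both the sample-size and the analysis text, as the equivalence boundary between DVD and face-to-face.

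**The concern.** A rule that rejects superiority whenever the interval contains +0.3 is a test of superiority by a margin: the lower limit must lie above 0.3. The sample size assumes a test against zero. With a planning difference of 0.38, the rule leaves 0.38 − 0.30 = 0.08 units to detect instead of 0.38.

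The DVD against usual care is one of the two comparisons for which the trial was built. A result such as an adjusted difference of 0.38 with a lower limit of about 0.21 (0.38 − 1.645 × 0.1005) would count as superiority under the test used for the sample size and as rejection under the analysis rule. The conclusion would depend on which part of section 8.1 was followed, and the quoted 90% and 92% describe only the first.

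**Working it through.** **Inputs, all from section 8.1.** Difference 0.38; SD 1.03; one-sided 5% (z = 1.645); analysed sizes 210, 210 and 105; 130 per arm for the stated DVD power; rule margin 0.3.

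**Formula.** SE = SD × √(1/n₁ + 1/n₂). Power ≈ Φ((difference − null)/SE − 1.645). Noncentral t results agree to within about 0.2 percentage points.

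**Step 1: standard errors.**
- 130 v 130: 1.03 × √(2/130) = 0.1278
- 210 v 210: 1.03 × √(2/210) = 0.1005
- 105 v 210: 1.03 × √(1/105 + 1/210) = 0.1231

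**Step 2: reproduce the protocol's figures (null 0).**
- 105 v 210: 0.38/0.1231 − 1.645 = 1.44, power 92.5% (noncentral t 92.4%). Stated: 92%.
- 130 v 130: 0.38/0.1278 − 1.645 = 1.33, power 90.8% (noncentral t 90.7%). Stated: 90%.

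A two-sided 5% test would give 87.0% and 84.5%, so the stated figures belong to a one-sided 5% test of zero difference.

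**Step 3: apply the written rule (null 0.3, so 0.08 to detect).**

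| Comparison | Power against 0 | Power against +0.3 |
|---|---|---|
| DVD, 210 v 210 | 98.4% | 0.08/0.1005 − 1.645 = −0.85, 19.8% |
| DVD, 130 v 130 | 90.8% | 0.08/0.1278 − 1.645 = −1.02, 15.4% |
| Face-to-face, 105 v 210 | 92.5% | 0.08/0.1231 − 1.645 = −1.00, 16.0% |

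**Step 4: what the rule demands.**
- Observed difference needed: 0.3 + 1.645 × 0.1005 = 0.465 (DVD) and 0.3 + 1.645 × 0.1231 = 0.503 (face-to-face). Both exceed the planning difference of 0.38.
- True difference needed for 90% power: 0.3 + (1.645 + 1.282) × SE = 0.59 (DVD) and 0.66 (face-to-face).
- Patients needed for 90% power at 0.38: about 2,840 per arm at 1:1.

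**Step 5: baseline adjustment.** ANCOVA multiplies the SD by √(1 − r²), where r is the correlation between baseline and 12-month scores. The protocol gives no r. Assuming 0.3 to 0.8, the SD falls to between 0.98 and 0.62.
- DVD: 21% to 37%
- Face-to-face: 17% to 29%

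**Step 6: the other planning scenario (difference 0.5, so 0.2 to detect).**
- SD 0.41 at the planned sizes: over 99% for both comparisons.
- SD 0.41 at that scenario's own sizes: 33% (13 v 13) and 34% (10 v 20).
- SD 1.03 at the planned sizes: 63% (DVD) and 49% (face-to-face).

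**The case against.** **The margin may be deliberate.** The synopsis hypothesises improvements that are clinically important, and section 8.1 ties 0.3 to clinical acceptability in the equivalence comparison. Requiring benefit beyond 0.3 is a coherent aim, and replacing it with zero would weaken the success criterion. That choice is the sponsor's, and this part of the objection stands. It does not remove the conflict: if the margin is meant, the power statements were calculated for another test.

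**One planning scenario survives the rule.** With 0.5 and SD 0.41, power at the planned sizes exceeds 99%. A reader might infer that a DVD which works as planned will probably be reported as not superior. The documents support that only for the 0.38/1.03 scenario. The 0.5/0.41 scenario is a weak defence, however. The protocol takes both values from change within a person and says that no widely accepted between-group value exists.

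**The low figures are unadjusted.** The analysis is baseline-adjusted, so 20% and 16% are not exact. This stands, and a range is given above. The range stays below 40%.

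**The stated 90% is not for 210 per arm.** A reader might set it beside the 20% and conclude that one became the other. They refer to different sample sizes. The matched pairs are 98% and 20%, or 90% and 15%.

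**The interval's direction and one-sided level.** A reader might also infer that the rule could be met by an interval bounded above and lying below +0.3, or that one-sided 5% testing is itself inconsistent. For superiority on a scale where higher is better, the lower limit is the only sensible reading. One-sided 5% is used consistently in the superiority sample size and analysis. Neither is part of this point.

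**Conclusion.** The contradiction is explicit and lies wholly within section 8.1, so a separate SAP would not excuse it. The superiority sample size tests against zero, and the superiority decision tests against +0.3, for which the analysis text gives no reason.

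The size of the problem is conditional. It rests on a true difference of 0.38, SD 1.03, the planned analysed numbers, a one-sided 5% level, and the rule read as a lower limit above +0.3. Under those assumptions the rule would miss a DVD effect of the planned size about four times in five, and a face-to-face effect slightly more often. Baseline adjustment over the assumed range does not bring power to an acceptable level. The documents do not show that the trial is underpowered under every planning assumption. They show that the stated power cannot be attached to the stated rule. Because this rule settles the primary comparison with usual care, it should be corrected before analysis.

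**What to change.** Reconcile the superiority sample-size text with the superiority analysis rule in one of two ways.

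1. **Test against zero, as the sample size does.** Replace the decision sentence with wording such as: superiority over usual care is declared if the lower one-sided 95% confidence limit of the baseline-adjusted difference in 12-month AQLQ (intervention minus usual care) is above 0; whether that limit also exceeds +0.3 is reported separately as a statement of clinical importance. The stated 92% for face-to-face then applies. For the DVD, 98% at 210 per arm could be added beside the 90% at 130. The cost is one sentence and no patients, and the formal success criterion becomes less demanding.

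2. **Keep +0.3.** State why 0.3 is the right margin against usual care, say that the lower limit must exceed it, and restate the superiority power as about 20% (DVD) and 16% (face-to-face) under 0.38 and SD 1.03. Any claim that baseline adjustment improves on this should state the correlation assumed. The cost is a justification and a restated power line, with low power openly accepted. Restoring 90% at 0.38 would need about 2,840 per arm at 1:1.

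### The repeated measures analysis lists baseline as a time point with no common baseline mean across arms; fitted that way, its arm contrasts are change scores, less precise than baseline-adjusted ones

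*Protocol*

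**What the plan says.** Section 8.1 handles baseline in two ways.

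- **Single-time-point analyses: baseline is a covariate.** In the superiority plan the 12-month AQLQ is compared "across the three arms with initial adjustment for baseline AQLQ score and then for other potential covariates". Continuous secondary outcomes are to be treated similarly, and the equivalence plan has them analysed "at 12 months before and after adjustment for baseline values and potential confounders".
- **Longitudinal analysis: baseline is one of the repeated measurements.** The superiority plan says "Since we have data on AQLQ, ACQ and HADS at four time points (baseline, 3, 6 and 12 months) a repeated measures analysis will be" carried out, and its stated purpose is change over time. The next sentence makes clear that arms are contrasted: "The 'usual care' arm will be compared to each of the DVD and 'face-to-face' breathing retraining arms in turn". The equivalence plan repeats the four-time-point wording: "HADS at four time points (baseline, 3, 6 and 12 months) a repeated measures analysis will be used to examine change".

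Neither plan says whether the arms are given a common baseline mean, or which contrast is to be reported.

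**The concern.** Patients are randomised after the baseline assessment, so the true arm difference at baseline is zero. A model that takes baseline as a fourth response and gives each arm its own baseline mean does not use that fact. Its arm-by-time contrast at any follow-up visit is then the difference between arms in change from baseline. That estimate carries the full chance imbalance at baseline, whereas ANCOVA removes only the part that predicts follow-up.

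Two things are at stake, both modest. First, section 8.1 gives the 3- and 6-month AQLQ, ACQ and HADS scores no other between-arm analysis, so any precision lost there is not recovered elsewhere. Second, at 12 months the longitudinal contrast and the ANCOVA would give different estimates for the same outcome, purely because of chance baseline imbalance.

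**Working it through.** **Inputs.** From the superiority sample size in section 8.1: difference 0.38, SD 1.03, one-sided 5%, 105 face-to-face and 210 usual care. Assumed, because the protocol gives no values: correlation rho between any two visits of 0.3, 0.5 or 0.7, and equal SD at all visits. As in the sample size section, power is against a null of zero difference.

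**1. The plan's own figure.**
SE0 = 1.03 × sqrt(1/105 + 1/210) = 0.1231.
Power = Phi(0.38/0.1231 − 1.645) = Phi(1.442) = 92.5% (92.4% by the noncentral t). The plan states 92%, so it reproduces.

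**2. Standard error of the 12-month contrast.**
Change from baseline: SE0 × sqrt(2(1 − rho)).
Baseline-adjusted: SE0 × sqrt(1 − rho²).
Ratio: sqrt(2/(1 + rho)).

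| rho | Change SE | Adjusted SE | Ratio | Power, change | Power, adjusted |
|---|---|---|---|---|---|
| 0.3 | 0.1457 | 0.1174 | 1.24 | 83.2% | 94.4% |
| 0.5 | 0.1231 | 0.1066 | 1.15 | 92.5% | 97.3% |
| 0.7 | 0.0954 | 0.0879 | 1.08 | 99.0% | 99.6% |

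For example, at rho 0.3: Phi(0.38/0.1457 − 1.645) = 83.2% and Phi(0.38/0.1174 − 1.645) = 94.4%.

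**3. DVD against usual care (210 v 210).** The ratio is the same, but power starts higher: 93.9% v 99.0% at rho 0.3, and 98.4% v 99.7% at rho 0.5.

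**4. What each four-response model gives.** The variance of the 12-month contrast was computed from the information matrix with complete data, in units of SE0². With separate baseline means it is 1.40, 1.00 and 0.60 at rho 0.3, 0.5 and 0.7, exactly the change score. With a common baseline mean it is 0.91, 0.75 and 0.51, exactly ANCOVA. The loss therefore comes from leaving the baseline means free, not from having baseline in the response.

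**5. If the baseline SD is smaller.** Let the baseline SD be k times the follow-up SD. The change-score variance is 1 + k² − 2k·rho, which exceeds 1 − rho² by (k − rho)². With an illustrative k = 0.8, the variances are 1.16 v 0.91, 0.84 v 0.75 and 0.52 v 0.51 at rho 0.3, 0.5 and 0.7. The SE excess falls to sqrt(1.16/0.91) − 1 = 13%, sqrt(0.84/0.75) − 1 = 6% and sqrt(0.52/0.51) − 1 = 1%.

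**The case against.** The strongest reply is that the protocol does not choose the inefficient model. It names time points and a purpose and leaves the model open; a statistical analysis plan normally supplies that detail, and its absence here is not a fault. This stands in part: nothing in the text rules out a common baseline mean or a covariate. But the point rests on what is stated, not on what is missing. Baseline is counted among the repeated measurements, arms are then compared, and the same section treats baseline as a covariate everywhere else. An analyst who follows the wording could readily fit four unconstrained responses.

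Section 3.1 also defines outcomes as change from baseline, within as well as between groups, which is a reason to keep baseline in the trajectory. That is fair, and the common-mean version of the fix preserves it.

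Four stronger readings are tempting, and the protocol does not support them:

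- **Listing baseline as a response must cost precision.** It need not: step 4 shows that a common baseline mean matches ANCOVA.
- **The treatment effect is diluted by a quarter.** An arm effect averaged over all four visits would turn 0.38 into 0.75 × 0.38 = 0.285. The plan never proposes that average; its stated aim of examining change points to time or arm-by-time terms.
- **The estimates are biased.** Under randomisation a change-score contrast is unbiased, only noisier.
- **The trial's main conclusions are weakened.** Superiority rests on the baseline-adjusted 12-month ANCOVA, and equivalence on the 12-month confidence interval. Neither uses the repeated measures analysis.

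**Conclusion.** The point holds as a minor improvement to a supplementary analysis. If the four-time-point wording is followed without a common baseline mean, the arm contrasts have standard errors roughly 8% to 24% larger than necessary over rho 0.7 to 0.3. For face-to-face against usual care that costs about 11 percentage points of power at rho 0.3, 5 at rho 0.5 and less than 1 at rho 0.7. These figures assume equal correlation between visits, equal SDs and complete data. The equal-SD assumption is doubtful, because entry requires an AQLQ below 5.5, which may narrow the baseline range. The AQLQ gap would then be smaller, provided that the SD ratio stays above rho. No stated sample size, power figure or primary decision rule changes.

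**What to change.** In both the equivalence and the superiority plan, replace the four-time-point sentence with one of two equivalent specifications:

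- a repeated measures model with the 3-, 6- and 12-month scores as responses, and arm, time, arm-by-time and the baseline score as fixed terms; or
- a model that keeps baseline as a response but gives all arms one common baseline mean, which also yields within-group change from baseline.

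In either case, state that the arm difference is reported at each follow-up visit. The cost is one sentence in each plan: the baseline scores are already collected, and no patients, visits or data are added. If within-group change from baseline is wanted from the same model, choose the second form, because the first does not estimate it directly.
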